The project is multidisciplinary, with multiple disciplines collaborating to achieve the common goal of improving motivation and long-term adherence to dietary-nutritional treatments. The research team has a strong track record in 3D image capture and processing, RGB-D sensor calibration and registration [22–27], as well as realistic modeling and visualization. The team also includes professionals in nutrition, psychology, and clinical assessment with experience in national and European projects focused on obesity, treatment adherence, and mental health.

Ethical Considerations

The study was approved by the Research Ethics Committee of the University of Alicante (code UA-2021-11-18, dated 18/11/2021). Prior to study participation and data collection, all participants provided written informed consent. Data will be handled in accordance with the GDPR and LOPDGDD regulations, with anonymization implemented through unique participant codes.

The following sections describe the study design, selected population, eligibility criteria, sampling strategy, sample size calculation, definition of included variables, measurement instruments, monitoring plan, and analysis strategies, along with potential limitations.

Study Design

A prospective longitudinal design with two assessment points was implemented: baseline (pretest) and post-intervention (posttest) after six months of treatment. The study comprised two groups: control and experimental. The control group received nutritional and physical activity education based on recommendations from a nutritionist. The experimental group received a specific, individualized dietary-nutritional intervention program combined with 4D virtual reality. Both groups were assessed for cognitive, clinical, and nutritional outcomes at baseline (pretest) and after six months of intervention (posttest).

To ensure sample representativeness and the generalizability of results, the sample size was calculated using the G*Power 3.1 statistical software. A statistical power of 80%, a medium effect size (0.5), and a significance level (α) of 0.05 were established. Under these parameters, at least 35 participants per group were required to carry out the intervention.

Selected Population

The sample consisted of a total of 133 Spanish volunteers, both men and women, aged between 22 and 67 years ($M = 47.11$ years; $SD = 9.38$). Participants were randomly assigned to one of the two groups (experimental or control).

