Capillary concentrations of cholesterol, glucose, and triglycerides were assessed using Accutrend® Plus with two drops of blood (15–40 μL) collected from different fingers using a lancet device (Accu-Chek® Softclix® Pro, Roche Diagnostics GmbH, Mannheim, Germany). Blood pressure was measured using an M7 Intelli IT sphygmomanometer (OMRON, M7 Corp., Kyoto, Japan).

4. Nutritional and Lifestyle Variables:

Questionnaires:

- Adherence to the Mediterranean Diet: Assessed using the PREDIMED questionnaire (Martínez-González et al., 2004).
- Physical Activity: Measured with the International Physical Activity Questionnaire (IPAQ) (Craig et al., 2003), which includes 7 questions on frequency, duration, and intensity (vigorous and moderate) of physical activity over the past 7 days, as well as walking and sedentary time on a workday.
- 24-Hour Dietary Recall: Patient food intake over the previous 24 hours, collected through three 24-hour recalls (two weekdays and one weekend or holiday).
- Food Frequency Questionnaire: Assessed frequency of food consumption (Martín-Moreno et al., 1993), aimed at recording the average number of times a specified amount was consumed throughout the year.

Data were collected through an adapted questionnaire administered via Google Forms.

5. Psychological Variables

- **Executive Functions:** This variable was assessed using the CogniFit General Cognitive Assessment Battery (CAB), a computerized neuropsychological test battery commonly used in research protocols for cognitive skills. The test duration ranges from 25 to 45 minutes and evaluates a wide range of cognitive domains, including cognitive flexibility, divided attention, planning, visual perception, auditory perception, spatial perception, contextual memory, short-term visual memory, non-verbal memory, short-term memory, working memory, short-term auditory memory, processing speed, naming, estimation, monitoring, reaction time, visual scanning, recognition, hand-eye coordination, focused attention, and inhibition. Scores range from 0 to 800 points, with higher scores indicating better cognitive performance.

Questionnaires:

- Premorbid Intelligence: Assessed using the Word Accentuation Test (TAP) (Del Ser et al., 1997), which estimates premorbid intelligence through the accentuation of 30 words. The number of correct answers corresponds to an estimated premorbid IQ based on WAIS-IV scoring.

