intervention. Anthropometric data and 4D images were also collected at both time points, as well as during individual follow-up sessions conducted to monitor progress and prevent relapses.

Monitoring Plan:

Potential adverse effects arising from the use of Virtual Reality (e.g., dizziness, discomfort, anxiety) and the dietary program (e.g., malnutrition, minor side effects) will be monitored. Adverse events will be recorded in a dedicated database and reported to the Ethics Committee if they are serious or unexpected. Participants will also have the right to withdraw from the study at any time without any consequences.

Data Analysis:

Data analysis is structured in two main phases, encompassing both the development of the predictive model and its clinical and psychological validation. A mixed strategy of advanced quantitative and computational analysis will be applied.

Data Preparation and Preprocessing

- Cleaning of clinical, anthropometric, psychological, and neuropsychological data.
- Standardization and normalization of variables (e.g., assessment scales, physical measurements).
- Coding of categorical variables (e.g., sex, experimental/control group).
- Outlier control and analysis of missing data (intent-to-treat analysis will be applied if missing data exceed 30%).

Classical Statistical Analysis

- **Between-group comparisons (control vs. experimental):**
 - t-tests or ANOVA for continuous measures.
 - Chi-square tests for categorical variables.
 - ANCOVA to adjust for covariates (age, sex, baseline BMI).
- **Longitudinal analysis:**
 - Repeated measures models (repeated measures ANOVA or mixed models).

- Study of changes between assessment points (0 and 6 months).

Multidimensional Predictive Modeling

- Use of multivariate regression models and machine learning to predict:
 - Body evolution (based on SMPL/STAR models).
 - Clinical parameters and psychological well-being.
 - Levels of adherence and motivation.
- Model training using data from the first period (M9) and validation in the second period.

Analysis of Predictive Psychological Variables

- Correlations between cognitive functions and adherence levels.
- Logistic/multiple regression analyses to identify significant predictors of therapeutic success.
- Evaluation of the mediating effect of psychological variables on physical and clinical changes.

Tools and Software

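### Predictors of therapeutic success are to be named by significance in regressions on at most 133 people, with no fixed candidate list (about 10 to 31 psychological scores), shrinkage or optimism correction

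*Combined protocol and SAP*

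**What the plan says.** Section 6, Data Analysis, under Analysis of Predictive Psychological Variables, lists three items: correlations of cognitive functions with adherence, "Logistic/multiple regression analyses to identify significant predictors of therapeutic success", and an assessment of mediation. The Summary likewise announces that psychological variables will be examined as predictors of treatment success.

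The sample is given under Selected Population: "The sample consisted of a total of 133 Spanish volunteers", both arms together. Loss to follow-up is listed as a limitation, without a rate.

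The candidate scores are described under Description of Variables, item 5. The CogniFit battery "evaluates a wide range of cognitive domains, including cognitive flexibility, divided attention, planning" and others, 22 in all. The same paragraph gives one scale: "Scores range from 0 to 800 points, with higher scores indicating better cognitive performance". The questionnaires that follow are TAP, CCE, ISP-20, BIS (three subscales), SF-12, BDI-II and SWLS.

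The plan does not define therapeutic success. For this analysis it gives no list of candidates, selection rule, significance threshold, shrinkage or validation. Training in one period and validation in a later one appears only under Multidimensional Predictive Modeling.

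**The concern.** Naming predictors by p-value in a small sample has two effects. Some null variables pass the threshold by chance, and the fitted model looks better in the data that produced it than it would in new patients. Both effects grow with the number of candidates relative to participants (or to events, in logistic regression), and the plan leaves that number open. Followed as written, the analysis can return named psychological predictors and an inflated AUC or R-squared even when no score carries information about success. Adjusting p-values would address the first effect but not the second.

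**Working it through.** **The plan's own figures.** No sample size, power or error rate is given for the predictor regressions. The only sample-size figure is 35 per group (effect size 0.5, power 80%, α 0.05). It is close to a two-sided paired t-test within one group, which needs 34. It was not derived for regression with many candidates, and nothing below depends on it.

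**Candidate count** (Description of Variables, item 5).
- CogniFit domains entered separately: 22 + TAP 1 + CCE 1 + ISP-20 1 + BIS 3 + SF-12 1 + BDI-II 1 + SWLS 1 = 31. With one BIS total the count is 29. Adding the two MBSRQ parts gives 33.
- CogniFit as one total: 1 + 9 = 10. With one BIS total it is 8, or 9 if SF-12 is also split in two.

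**Participants per candidate.** 133/31 = 4.3. With an assumed 40% success rate there are 0.40 × 133 = 53.2 events, so 53.2/31 = 1.7 events per candidate, or 53.2/10 = 5.3 with ten scores.

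**Chance of at least one false predictor, simple bound.** With k independent null candidates each tested at 0.05, the chance is 1 − 0.95^k:
- k = 8: 0.34
- k = 9: 0.37
- k = 10: 0.40
- k = 31: 0.80, with 31 × 0.05 = 1.55 false predictors expected

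**Simulation of the named regressions.** Normal scores, an outcome unrelated to any of them, all scores entered together, two-sided 0.05, n = 133. For logistic regression, success is 40% and pairwise correlation 0.3 unless stated.

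| Scores entered | Linear: at least one false predictor | Logistic: at least one false predictor | Logistic: mean apparent AUC |
|---|---|---|---|
| 8–10 | 38–39% (10 scores) | 34–41% in most runs | 0.64–0.66 |
| 31 | 74–76% | 86–93%, about 90% | 0.79 |

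The true AUC is 0.50 throughout. One separate set of runs with 10 scores gave 45%. With 31 scores the mean number of false predictors is about 1.5 to 1.6 (linear) and 2.5 to 2.9 (logistic).

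**Null R-squared.** The expected value is k/(n − 1): 31/132 = 0.23, or 10/132 = 0.08.

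**Sensitivity, 31 scores.**
- Success of 30–50%: logistic 89–91%.
- Backward elimination in linear regression, correlations 0 to 0.7: 82–92%, with 1.9 to 2.5 false predictors.
- 30% lost (0.70 × 133 = 93 participants): linear 71–73%, logistic 92–93%, apparent AUC 0.85–0.86.
- Scores tested one at a time: 67% at correlation 0.3, 52% at 0.5 and 34% at 0.7. The expected number of false predictors stays near 1.5.

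**Undefined outcome.** If three independent definitions of success were tried, the simple bound becomes 1 − 0.95^24 = 0.71 with 8 scores and 1 − 0.95^30 = 0.79 with 10.

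**The case against.** The strongest objection concerns the count. Nothing says that 22 domain scores enter the regression. The battery is introduced as measuring a single variable with one 0–800 range, and the plural reference to cognitive functions belongs to the correlation item. A reader might infer that about 31 candidates are planned and that false predictors are therefore very probable. The documents do not support that as a settled fact. With one CogniFit total the chance is about 34–40% for one outcome. This stands, and it is why the size is given as a range. It does not remove the problem, because nothing in the plan limits the count.

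The linear half of the item is also less affected than the logistic half. A null R-squared of 0.23 corresponds to an adjusted value of 1 − (101/132) × (132/101) = 0, and the overall F-test keeps its 5% rate. That helps only if adjusted R-squared and the overall test are what is reported, and the plan does not say so.

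The plan does contain validation, and that part covers regression models for adherence and motivation. It stands under a different heading, however, and nothing extends it to the search for psychological predictors.

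A reader might also infer that predictors selected here feed the personalised body model. The protocol says that psychological variables enter that model, but not that they are chosen by these p-values. The harm shown is therefore confined to this secondary analysis.

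**Conclusion.** The point holds in conditional form. The plan makes significance the criterion for naming predictors and controls neither the number of candidates nor the optimism of the fit. At n = 133 the chance of at least one false predictor is about 34–40% with 9 to 10 scores, and about 75% (linear) to 90% (logistic) with 31. Apparent AUC is about 0.65 and 0.79 respectively against a true 0.50, and expected null R-squared with 31 scores is 0.23.

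These figures assume that no score predicts success, that all scores are entered together and that each is tested at 0.05. The plan states 0.05 only for the sample size. The logistic results also assume 40% success and correlation 0.3, since the plan gives neither. Loss to follow-up raises the apparent AUC, whereas one-at-a-time testing of correlated scores lowers the chance of any false predictor. This is a secondary analysis, so the sponsor should correct it, but the comparison of the two arms is not affected.

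**What to change.** Replace the regression item with the following:

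1. One main model for therapeutic success, as the sponsor defines it in advance. Keep the outcome continuous where it is continuous. The choice of outcome is the sponsor's, given that the project's stated aims are motivation and adherence.
2. The main model contains arm, age, sex, baseline BMI and a short list of baseline psychological scores fixed before analysis, using the CogniFit total rather than the 22 domains.
3. Any remaining candidates enter only one penalised model (ridge or lasso).
4. Report R-squared or AUC corrected for optimism by bootstrap, resampling participants and repeating the whole modelling procedure in each resample.
5. Make no predictor claim from p-value selection alone, and label findings outside the main model exploratory.

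The cost is a revised paragraph and a few lines of code in R or Scikit-learn, both already listed under Tools and Software. No new data or visits are needed. The downside is that fewer variables can be named as predictors and the reported fit will be lower.

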The general objective of **Tech4D-Predict** is to develop methods for the acquisition and visualization of 4D human body models, aimed at supporting dietary-nutritional interventions and enhancing long-term patient motivation and adherence to treatment. Furthermore, the study will evaluate the impact of this tool on cognitive function and psychological well-being.

In pursuit of this overarching objective, the following specific aims are defined:

- **Specific Objective 1: Development of flexible methods for the acquisition of 3D human body models. The goal is to equip the acquisition system with flexibility, robustness, and portability without compromising accuracy.**

Flexibility refers to the system's ability to tolerate subject movements during the acquisition process, and even to leverage these movements to capture multiple views of the subject in order to complete the 3D model. The ultimate aim is to progress towards 3D self-portraits. Portability involves the ability to easily transport the system/device, using a compact set of RGB-D cameras integrated into a readily transportable device. Robustness refers to the stability of the acquisition system against potential movements that could affect camera calibration, as well as variations in acquisition conditions (e.g., lighting).

- **Specific Objective 2: Development of methods for obtaining multidimensional predictive models of morphological and clinical body evolution during dietary-nutritional treatment.**

The aim is to move beyond 4D memory-based models, which visualize the morphological changes experienced by the body during treatment, towards multidimensional predictive models that anticipate potential morphological changes and clinical outcomes for specific patient profiles. These predictions will be based on prior experience, the 4D morphological models of patients from the current project, and their corresponding clinical data.

- **Specific Objective 3: Evaluation of the effectiveness of multidimensional predictive model visualization on patient motivation during treatment and its impact on long-term adherence.**

The primary aim of this objective is to assess the impact of the methods developed in **Specific Objectives 1 and 2**—related to 4D model acquisition and visualization, and the construction of predictive models of clinical and morphological evolution—within a real clinical setting through a patient intervention.

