Accordingly, this objective encompasses the implementation of a clinical trial **with two intervention groups (experimental and control)** designed to evaluate the effect

of a personalized intervention combining the benefits of 4D body modeling and virtual reality techniques with a dietary-nutritional treatment based on the Mediterranean Diet. The intervention aims to enhance motivation for change, treatment adherence, and health parameters in overweight and obese patients.

Furthermore, this study will allow systematic collection of clinical, anthropometric, nutritional, and psychological data, which will be integrated into the multidimensional predictive model to improve its precision and personalization capabilities.

Specifically, the clinical trial includes the following specific aims:

- To study how a 4D computer vision model combined with virtual reality technology can improve clinical assessment, the analysis of temporal morphological changes of the human body, and adherence to dietary-nutritional treatment.
- To evaluate whether adherence to an intensive multifactorial dietary-nutritional treatment based on the Mediterranean Diet, supported by immersive 4D virtual reality technology, leads to improvements in cognitive functioning.
- To analyze the impact of a nutritional intervention program based on the Mediterranean Diet and the use of virtual reality on body image perception.
- To determine whether a combined intensive intervention—based on the Mediterranean Diet and 4D virtual reality technology—can improve patients' overall health.

6. Methodology

The intervention follows a multidisciplinary approach that combines clinical, psychological, and technological assessment of overweight or obese patients, using innovative tools based on 3D body reconstruction and predictive modeling.

Challenges to Address and Technical Phases

1. 3D Model Acquisition

3D images of the body are captured from multiple viewpoints using RGB-D sensors, due to their precision, low cost, and portability. The images are aligned using articulated rigid registration techniques, enabling the construction of a complete body model. The research team has developed advanced RGB-D camera alignment methods, optimizing accuracy under real-world capture conditions [22–24].

2. 4D and Predictive Model Generation

Starting from 3D models obtained at different stages of the treatment, deformable

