- Emotional Eating: Measured with the Emotional Eater Questionnaire (CCE) (Garaulet et al., 2012). Higher scores indicate greater influence of emotions on

food choices and eating habits.

- Prefrontal Symptoms: Assessed using the Prefrontal Symptoms Inventory (ISP-20) (Ruiz et al., 2012); the short version (Pedrero-Pérez et al., 2015) is a self-report questionnaire measuring cognitive, emotional, and behavioral alterations in daily activities.
- Impulsivity: Measured with the Barratt Impulsiveness Scale, BIS-II (Barratt, 1959), comprising 30 items divided into three subscales: cognitive impulsivity (8 items), motor impulsivity (10 items), and non-planning impulsivity (12 items).
- Health-Related Quality of Life: Assessed using the Short Form-12 Health Survey (SF-12) (Ware et al., 1996).
- Depression: Measured using the Beck Depression Inventory (BDI-II) (Beck, Steer & Brown, 1996).
- Life Satisfaction: Measured using the Satisfaction With Life Scale (SWLS) (Diener et al., 1985).

All questionnaire data were collected via Google Forms.

6. Technological and Body Image Variables

- **Body Image:** Assessed using the Body Self-Relations Questionnaire (MBSRQ – reduced Spanish version) (Botella et al., 2009). The instrument contains 45 items divided into two distinct parts: one evaluating general body image and another assessing satisfaction with specific body areas.
- **3D and 4D Images:** The 4D model represents morphological changes over time. Using wide-spectrum, low-cost 3D acquisition technologies (RGB-D sensors), a 4D model was constructed as the core of a human body visualization system, enabling accurate and realistic visualization over time. Throughout the intervention, morphological 3D images of participants were obtained, allowing them to observe their evolution through immersive Virtual Reality (VR) (only the experimental group observed these changes).

Morphological 4D images of participants in each session were captured using the 3D machine, composed of RGB-D devices for 3D image acquisition.

All anthropometric and clinical measurements were collected at the ALINUA Nutrition and Food Clinic, certified as a healthcare center affiliated with the Faculty of Health Sciences at the University of Alicante.

All questionnaires and the neuropsychological battery were administered at two time points: at the start of the program (initial session) and after six months of

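### The predictor analyses name neither randomised arm nor the time point of the scores, so an arm effect on six-month or change scores could be reported as a predictor or correlate of success

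*Combined protocol and SAP*

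**What the plan says.** The combined protocol and SAP, section 6 (Methodology), under Data Analysis, has a block on predictive psychological variables with three one-line items:

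- The first is a plain association analysis: "Correlations between cognitive functions and adherence levels".
- The second covers the prediction models: "Logistic/multiple regression analyses to identify significant predictors of therapeutic success".
- The third, on mechanism, is worded as follows: "Evaluation of the mediating effect of psychological variables on physical and clinical changes".

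No item lists model terms, mentions randomised arm or gives the time point of the scores. Therapeutic success is not defined, and the mediation item does not name its exposure. Adjustment covariates (age, sex, baseline BMI) are named only for the ANCOVA under the between-group comparisons. The preprocessing list codes study group as a categorical variable but does not say which models use it.

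Three other statements bear on the point:

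- Under Study Design, the control group receives education on nutrition and physical activity, and the experimental group receives an individualised diet programme with 4D virtual reality.
- In section 5, the trial aims to improve motivation, adherence and health, and to test whether adherence to the diet treatment, "supported by immersive 4D virtual reality technology, leads to improvements in cognitive functioning".
- The variable descriptions end with the collection schedule: "All questionnaires and the neuropsychological battery were administered at two time points". These are baseline and month six, so scores from both times will be available.

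**The concern.** If the experimental programme raises both a psychological score and an outcome, the two are correlated across the whole sample even when they are unrelated among participants on the same programme. Unless arm is in the model, that correlation is read as information about patients: people with better cognition adhere better, or succeed more often. It is in fact the treatment effect seen twice.

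The first item is the most exposed. It relates two quantities that the programme is meant to change, and a simple correlation has no place for an arm term. Because the plan is silent on both arm and timing, it permits this version of the analysis and lets the choice be made after the data are seen.

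At stake is the interpretation of the supporting predictor analyses. The between-group comparisons are not affected.

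**Working it through.** The plan gives no figure for these analyses, so there is none to reproduce.

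**Inputs.** The total sample is 133 (Selected Population). Allocation is random to two groups with no stated ratio; I assume 1:1. The only effect size in the documents is 0.5, in the sample size statement, and it is not tied to these scores. The arm shifts below are therefore assumptions, shown as a range. No dropout is assumed.

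**Induced correlation.** Let arm shift the score by d1 and the outcome by d2, in within-arm SD units, with zero correlation within each arm. A 1:1 arm indicator has variance 1/4, so the covariance across arms is d1·d2/4 and the variances are 1 + d1²/4 and 1 + d2²/4:

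r = (d1·d2/4) / √[(1 + d1²/4)(1 + d2²/4)]

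For d1 = d2 = 0.5: 0.0625 / 1.0625 = 0.059. For 1.0 and 0.5: 0.125 / √(1.25 × 1.0625) = 0.108. For 1.0 and 1.0: 0.25 / 1.25 = 0.200.

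**False-positive rate.** Simulated trials of 133, two-sided test of the correlation at 0.05, without arm and then with arm partialled out:

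| Shift in score / outcome (SD) | Induced r | Without arm | With arm |
|---|---|---|---|
| 0.3 / 0.3 | 0.022 | about 6% | about 5% |
| 0.5 / 0.5 | 0.059 | 10% | about 5% |
| 0.8 / 0.8 | 0.138 | 35% | about 5% |
| 1.0 / 0.5 | 0.108 | 24% | about 5% |
| 1.0 / 1.0 | 0.200 | 65% | about 5% |

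At 70 participants (twice the stated minimum of 35 per group), the unadjusted rate is 8% at 0.5/0.5 and 21% at 0.8/0.8.

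**Baseline scores.** Randomisation makes d1 = 0 in expectation, so the induced correlation is zero. The simulated rate without arm is 4.9–5.0%. What is lost is precision: omitting arm leaves (d2²/4)/(1 + d2²/4) of the outcome variance in the residual, which is 5.9% for d2 = 0.5 and 20% for d2 = 1.0. Standard errors widen by a factor √(1 + d2²/4), that is 1.03 to 1.12.

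**Arm-by-predictor term.** With a standardised predictor and 1:1 arms, the standard error of the slope difference is about 2/√133 = 0.173. The difference detectable with 80% power is (1.960 + 0.842) × 0.173 = 0.49 SD per SD. Power is 30% for a difference of 0.25 and 82% for 0.50.

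The simulation covers continuous outcomes. The logistic case was not simulated.

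**The case against.** The strongest reply is that a reader might infer from the silence that the plan pools the arms and leaves arm out. It says neither. The three items give no model terms at all, not even age or sex, and group is coded as an analysis variable. This stands: the defect is an unspecified choice, not a stated wrong one.

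Second, the false-predictor mechanism also needs post-baseline scores, and the plan does not say that it will use them. This also stands. With baseline scores the error rate is nominal and the gain from adding arm is precision. In a logistic model, omitting arm also moves the odds ratio towards 1, but that reflects a marginal rather than a conditional odds ratio and does not create a false predictor.

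Third, the larger rates need arm shifts of about 1 SD, which nothing in the documents supports. At 0.3 SD the inflation is negligible.

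Fourth, a reader might infer that the gap defeats Specific Objective 2, which seeks "multidimensional predictive models that anticipate potential morphological changes and clinical outcomes for specific patient profiles". The documents do not support that. The objective belongs to the separate block on multidimensional predictive modelling, and section 6 describes the body model as conditioned on dietary-nutritional and psychological variables and as projecting different intervention scenarios, so treatment is an implied input there. Nor does Objective 2 promise to identify who gains more from the experimental programme.

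What the reply does not remove is that six-month scores are collected, that the programme is expected to move them, and that a plain correlation carried out as written would not account for arm.

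**Conclusion.** The point holds as a gap in specification with a definite consequence. The plan does not say that the predictor analyses include randomised arm, or which time point supplies the scores. If arm is omitted and six-month or change scores are used, an association that is only the arm effect can be declared significant. The rate is about 10% at the one effect size the documents mention, applied to both score and outcome, and ranges from about 6% to 65% over the assumed shifts, against about 5% with arm included. This rests on 1:1 allocation, 133 analysed participants, no within-arm association and assumed shifts. With baseline scores there is no inflation. The plan should be changed because the remedy costs almost nothing, but the documents do not show that a biased analysis has been chosen.

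**What to change.** In the block on predictive psychological variables, state that:

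1. Randomised arm is a covariate in every predictor regression.
2. Simple correlations are replaced by arm-adjusted (partial) or within-arm correlations.
3. Baseline scores are used when the claim is prediction of therapeutic success, and therapeutic success is defined.
4. Where six-month or change scores are used, for example to relate adherence to cognitive change, the arm term stays and the result is described as an association. A blanket restriction to baseline scores would block a stated aim of the trial.
5. Arm is the exposure in the mediation analysis.

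An arm-by-predictor term is optional. It is needed only if the report will say who benefits more from the experimental programme. In that case, name a short list of predictors in advance and label the results exploratory, because 133 participants give 80% power only for slope differences of about 0.5 SD per SD.

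The cost is a few sentences and one degree of freedom per model, with one more for each optional interaction. No data collection changes.
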